12.7 Expedited Reporting

Adverse events that are assessed as serious, drug-related, and are evaluated by the site PI as unexpected, per the current product label, qualify for expedited reporting to the FDA. For the events identified as serious, drug-related, and unexpected, site investigators are required to complete and submit the MedWatch Online Voluntary Reporting Form (3500) at <https://www.accessdata.fda.gov/scripts/medwatch/>.

12.8 Acute Chest Syndrome

- 1) Reported Acute Chest Syndrome (ACS) events will be reviewed to verify the diagnosis of ACS by an adjudication committee consisting of study site investigators specializing in hematology and emergency medicine within 15 days of event entry into the Hospitalization eCRF. Each reported ACS event will be reviewed by two members of the committee. If they do not agree, a third member of the committee will review the event and the result of the majority will be recorded. Committee members will not review events from their site. The adjudication results will be entered into the ACS eCRF by the Clinical Coordinating Center within 5 business days of the completed adjudication.

13. STATISTICAL CONSIDERATIONS

13.6. Overview

Detailed description of the plan for statistical analysis of each endpoint will be detailed in a Statistical Analysis Plan (SAP) that will be prepared after the final study protocol is approved. The SAP will be prepared by the DCC senior statistician under [name] supervision.

Descriptive statistics will be used to summarize patient socio-demographic and clinical characteristics. The analyses of primary and secondary outcomes as well as the summary description of pain-related side effects and safety will be carried out by the DCC statistical service. Means, standard deviations, medians, 25th and 75th percentiles, minimum and maximum will be presented for continuous variables; the number and frequency of patients in each category will be presented for nominal variables. For all analyses, a two-sided p-value ≤ 0.05 will be considered statistically significant. Analyses will be performed using SAS version 9.4 or higher software (SAS Institute, Inc., Cary, NC).

Multiple Comparisons: With the pre-specified primary and secondary analyses, we

recognize that there is a multiplicity of analyses to be performed, which leads to an increased probability that at least one of the comparisons could be "significant" by chance. There are adjustments (e.g., based on the Bonferroni inequality) that can be used to preserve the overall type I error level. To attempt to adjust for the effects of the repeated significance testing that will occur as part of potential interim monitoring (discussed below), plus to adjust for the multiplicity of secondary outcomes, would require that very small significance levels be used for every comparison. Rather than taking this approach we will be conservative in the interpretation of secondary analyses, taking into account the degree of significance, and looking for consistency across outcomes. The actual p-value for each comparison will be reported to aid in the overall interpretation. In addition to the pre-specified primary outcome, we will use pre-specified secondary outcomes and pre-specified subgroups to help avoid over-interpretation and to help guard against and reduce the problems inherent with multiple testing.

13.7. Clinically Significant Difference, Sample Size and Power Justification

Clinically Significant Difference: The primary outcome for this superiority study is the change in pain scores from the time of placement in a treatment area to the time of disposition (hospital admission, discharged home, assigned to observation status) or a maximum treatment duration of 6 hours, whichever comes first between, two possibly effective treatments. The primary outcome will be measured using a 0-100 mm visual analog scale. Since both analgesic protocols may significantly decrease pain, we chose 14 mm as the minimal clinically significant difference between the two analgesic protocols based on 1) the literature supporting an additional 14 mm pain reduction as clinically important relative to the weight-based analgesic protocol in patients with an initial high pain score¹⁷ and 2) data from our R34 trial. Todd et al.¹⁸ first explored the concept of "minimally clinically significant" change in pain using a 0-100 mm visual analog scale (VAS) in the setting of an urban county hospital emergency department with a Level I trauma center. In that investigation, the numeric change on the VAS was compared to the patients' subjective change in pain. The investigators found that a mean change of 13 mm on a VAS was estimated with a patient assessment of a "little less" pain, thus an estimation of clinical significance in pain reduction. In a 2nd ED study¹⁹ of 74 subjects with vaso-occlusive sickle cell crisis, a change of 13.5 mm was estimated as the minimum clinically significant change based on patients describing their pain as "a little better," validating Todd's findings. Both of these studies are based on one treatment group and this clinical minimal change can only be used as clinically significant difference between two groups if the reference group is assumed to have zero change. Because the weight-based analgesic protocol has non-zero pain reduction based on the R34 study, 13 mm is not used for the clinically significant difference between the two analgesic protocols. The IMPROVE trial²⁰ was designed to compare two patient-controlled analgesia (PCA) dosing strategies in adults and children with SCD and it used 25 mm as the clinically significant difference between the two strategies in their design. Most relevant to our proposed study, Bird and Dickson¹⁷ argued that the clinically significant change for patients with high initial levels of pain, especially with a VAS between 67-100 mm, required a larger improvement in pain scores. Specifically, they reported that patients with "a lot less" pain had a mean (95% CI) VAS pain reduction to be 48 mm (43, 53) if initial VAS core is within 67-100 mm. We expect that the SCD patients with ED visit due to VOE will have a high initial pain score and this was the case in the R34 study where nearly all of the patients in our R34

reported an arrival pain score between 67-100 mm. Thus, it is important that patients must experience a reduction of at least 43 mm from arrival to discharge in order to feel “a lot less” pain. In the R34 study where we restrict data to the 1st ED visit, patients in both analgesic protocols achieved a clinically meaningful change of 13 mm in pain scores from arrival to discharge (Table 3).

Table 3. Primary and Secondary Outcomes Observed from the R34 Study

Outcomes	Total (N=52)	Patient-specific Analgesic Protocol (N=26)	Weight-based Analgesic Protocol(N=26)
Primary outcome: Change in pain scores from arrival to discharge or inpatient admission (maximum elapsed time of 6 hours); n, mean \pm SD	n=48, 36 \pm 30	n=25, 43 \pm 31	n=23, 29 \pm 27
Secondary Outcomes:			
Length of the 1 st ED visit in minutes, mean \pm SD	278 \pm 78	302 \pm 70	254 \pm 79
Hospital admission in the 1 st ED visit, %	38.5%	34.6%	42.3%
Returned ED visit within 7 days of the 1 st ED visit, %	15.7%	19.2%	12.0%
Hospital admission within 7 days of the 1 st ED visit, %	9.8%	11.5%	8.0%

However, to justify the additional workload of patient-specific analgesic protocols it is important to justify how much better improvement in pain scores is achievable and meaningful, especially in the population with high arrival pain score when compared to a weight-based analgesic protocol. The mean VAS pain reduction was 29 mm in the weight-based analgesic protocol in the R34 study. Thus, an additional 14 mm in pain reduction will bring the pain reduction to 43 mm (achieved in the patient-specific group in the R34 study), which is the pain reduction needed (based on the lower bound of 95% CI7) to have “a lot less” pain for patient with an initial high pain score. Therefore, 14-mm difference in pain reduction between the two analgesic protocols is chosen as the meaningful and clinically significant difference for patients experiencing SCD VOE with an initial high pain score.

The previous R34 study indicated that 49% of the subjects had at the ED visit over the 13 months of enrollment. The observed missing data rate in pain score reduction is 8%, due to either missing pain score at arrival or at discharge. No enrolled patient died in the previous R34 study. The overall SD of the pain score reduction from arrival to discharge was 30, with 27 and 31 in the weight-based and patient-specific analgesic protocol groups, respectively. Therefore, our assumptions of 10% missing data rate and a SD=31 in pain score reduction are conservative. With a 24-month enrollment period in this study, nearly double the enrollment time in the R34 study, it is conservative to assume that 50% of the randomized subjects will have a qualifying ED visit within the 24-month enrollment period. Thus, a total target sample size of 230, with 460 randomized subjects, is a reasonable and conservative estimate. As detailed in Table 4, we varied the missing data rate from 5%-10%, the SD of pain score reduction from 30-33, and percent of randomized subjects with an ED visit from 50% to 75%. All scenarios give 85% or higher power to detect a 14-mm clinically significant difference with the target sample size of 230 in the ITT population at 0.05 level. While the R34 study didn't have sufficient power to detect a 14-mm difference, the proposed study will have 90% power to detect this difference if outcome data is similar to the R34 study. Our sample size calculation assumes the pain score reduction follows a normal distribution based on data from the R34 study that indicated that the normality assumption was not violated.

Power calculation for the secondary outcomes are performed for the target sample size of 230 at 0.05 level. We do not expect any missing data in the secondary outcomes, as seen in the R34 study. For the length of ED stay from arrival to discharge, we have 83% power to detect a 30-minute difference in length of ED stay between the two analgesic protocols, assuming SD of 78. In the R34 study restricting to the first ED visit, the mean (SD) length time from arrival to discharge was 278 minutes (SD=78). For the secondary outcome of (yes/no) hospital admission in the 1st ED visit, returned ED visit or hospital admission within 7 days of the 1st ED visit, we use 15% as clinical significant difference. We have 64%, 78% and 94% power to detect a 15% difference in hospitalization rates in the 1st ED visit, in rates of returned ED visits within 7 days, and in rates of hospital admission within 7

days, respectively, with 0.05 type I error. We have assumed that hospitalization rates are 35% and 50%, the 7-day returned ED rates are 30% and 15%, and 7-day hospitalization rates are 20% and 5%, in the patient-specific and weight-based analgesic protocols, respectively. The assumptions on the hospitalization rates and the return ED visit rates are based on the observations in the R34 study.

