8.2. Randomization and Patient Analgesic Protocols

After patients have provided informed written consent, they will be randomized to either

the weight-based analgesic protocol or a patient-specific analgesic protocol that will be developed by their hematologist/sickle cell team. A 1:1 treatment allocation will be used with site as the stratification variable. A computer-generated permuted block randomization schedule with stratification by clinical site will be prepared by the DCC senior statistician with block size randomly chosen that will not be revealed to investigators. This scheme provides chronological balance during enrollment with respect to the number of patients allocated to each treatment arm, and thus balances the treatment groups with respect to possible changes in the mix of patients over time. For the sites, the randomization will be available through the password protected and customized web-based electronic data capture (EDC) system. The EDC will be maintained by the DCC data management team. Treatment plans can be updated as needed by the hematologist.

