4.2. Secondary Endpoints

The secondary endpoints are as follows:

- ED length of stay
- Hospitalization for pain control
- Return ED visits
- Hospitalizations, if not admitted to hospital on ED visits
- Re-hospitalizations, if admitted to hospital on ED visit and was discharged – we ignore those still hospitalized within 7 days of the index ED visits
- Day hospital visits, regardless admitted to hospital on ED visits or not
- A composite of return ED revisits or hospital re-admissions or day hospital visits (binary outcome with a cutoff at zero)

Methods of the final analyses: For the ED length of stay (from ED admission to discharge), a linear regression analysis similar to the primary outcome will be used to compare the length of stay between the two arms. For the hospital admission rate, chi-square test will be used to compare the admission rates between the two groups. For the count data (e.g., ED re-visits or hospitalizations or re-hospitalizations, or day hospital visits for VOE within 7 days after the recorded ED visit), it will be first evaluated by collapsing the data into a binary outcome with a cut off at zero and a chi-square test or Fisher exact test (if frequency is below 5 or less) to compare the re-admission rates or rate of a returned ED visit between the two groups. If there is sufficient spread in the count data, a Poisson regression approach will be used to test for protocol differences in the count outcome. (section 13.9.)

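### The 94% power stated for 7-day hospitalization belongs to a comparison of all 230 patients and does not carry over to the two subset endpoints that the SAP tests in its place

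*Protocol*

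**What the plan says.** Protocol 13.7 states the basis of its secondary-endpoint power: "Power calculation for the secondary outcomes are performed for the target sample size of 230 at 0.05 level". It adds "We do not expect any missing data in the secondary outcomes", so the full 230 enter the calculation. It then reports: "We have 64%, 78% and 94% power to detect a 15% difference in hospitalization rates in the 1st ED visit". The sentence goes on to link the 78% to return ED visits within 7 days and the 94% to hospital admission within 7 days. The assumed rates, patient-specific versus weight-based, are 35% versus 50% for index admission, 30% versus 15% for 7-day ED return and 20% versus 5% for 7-day hospitalization.

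Protocol section 11 (secondary endpoints) and 13.9 define and analyse 7-day hospitalization without restricting it by what happened at the index visit.

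The SAP does restrict it. The SAP synopsis, SAP 4.2 and Table 17.1 list two endpoints in its place. The first is "Hospitalizations, if not admitted to hospital on ED visits". The second is re-hospitalization in patients who were admitted and then discharged, with the rule that "we ignore those still hospitalized within 7 days of the index ED visits". Table 17.1 has no row for 7-day hospitalization in all patients. The SAP repeats the power statement for the primary endpoint only (2.4 and 4.1) and gives none for these two endpoints.

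**The concern.** The only power figure in either document for 7-day hospitalization is 94%, and its denominator is every enrolled patient. The hospitalization endpoints that will be tested and reported each use part of that denominator, and the protocol's own index admission rates show how small the parts are.

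The assumed direction matters. The protocol assumes more 7-day hospitalization in the patient-specific arm (20% versus 5%), so a null result here would reassure about the arm that the trial hopes to show superior. At 93.6% power, the chance of missing that difference is about 6%. If the same rates held inside the subsets, it would be about 27% (100 − 72.5) in patients not admitted and about 37% (100 − 63.1) or more in patients admitted. Anyone reading a null subset result against the 94% would credit it with too much.

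**Working it through.** **Inputs.** N = 230 (Protocol 13.7). Allocation: "A 1:1 treatment allocation will be used with site as the stratification variable" (Protocol 8.2), so 115 per arm. Test level: "a two-sided p-value ≤ 0.05 will be considered statistically significant" (Protocol 13.6). Rates as listed above (Protocol 13.7).

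**Formula.** Two-proportion power, normal approximation with pooled variance under the null:

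power = Φ[(|p1 − p2| − 1.96·s0) / s1]

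where s0 = √[p̄(1 − p̄)(1/n1 + 1/n2)], s1 = √[p1(1 − p1)/n1 + p2(1 − p2)/n2], and p̄ = (n1·p1 + n2·p2)/(n1 + n2).

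**Step 1: reproduce the stated figures at 115 per arm.**
- 20% versus 5%: p̄ = 0.125, s0 = 0.0436, s1 = 0.0425; (0.15 − 0.0855)/0.0425 = 1.52; power 93.6% (stated 94%).
- 35% versus 50%: 63.5% (stated 64%).
- 30% versus 15%: 78.1% (stated 78%).

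All three match, which identifies both the method and the denominator. Other methods for 20% versus 5% at 115 per arm give 92.3% (Fisher exact) to 95.1% (exact chi-square).

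**Step 2: expected subset sizes from the assumed index admission rates.**
- Not admitted: 0.65 × 115 = 74.75 versus 0.50 × 115 = 57.5.
- Admitted: 0.35 × 115 = 40.25 versus 0.50 × 115 = 57.5, before removing patients still in hospital.

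**Step 3: power if 20% versus 5% is assumed to hold inside each subset.** This is an assumption; the documents give these rates for all patients only.
- Not admitted: s0 = 0.0599, s1 = 0.0545; (0.15 − 0.1174)/0.0545 = 0.598; power 72.5%. Exact chi-square gives 73% to 76%, Fisher 70% to 72%.
- Admitted, all discharged in time: s0 = 0.0648, s1 = 0.0693; (0.15 − 0.1269)/0.0693 = 0.333; power 63.1%. Exact chi-square gives 63% to 66%, Fisher 58% to 59%.
- Admitted, if 10%, 25% or 50% are still in hospital and are dropped (assumed range): 58.8%, 51.7% or 38.2%.
- With the R34 index admission rates (34.6% versus 42.3%, Protocol Table 3) in place of 35% versus 50%: 76.8% not admitted, 58.5% admitted.

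**Step 4: power if only the overall rates are kept.** Overall, 20% and 5% of 115 give 23 and 5.75 expected events. Let a share of these fall in patients not admitted, the same share in both arms (an assumption), with all admitted patients discharged in time.

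| Share of events in not admitted | Not admitted: rates | Power | Admitted: rates | Power |
|---|---|---|---|---|
| 50% | 15.4% v 5.0% | 47.5% | 28.6% v 5.0% | 88.7% |
| 65% | 20.0% v 6.5% | 60.6% | 20.0% v 3.5% | 73.6% |
| 75% | 23.1% v 7.5% | 68.5% | 14.3% v 2.5% | 58.6% |
| 90% | 27.7% v 9.0% | 78.5% | 5.7% v 1.0% | 29.5% |

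For example, at 50% the rates in patients not admitted are 11.5/74.75 = 15.4% and 2.875/57.5 = 5.0%. Every row agrees with the protocol's overall 20% versus 5%. Neither subset reaches 94% in this range, and what one gains the other loses.

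**The case against.** Several points on the other side are fair.

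- A reader might infer that the 94% is a miscalculation. It is not. It reproduces, and it is correct for the unrestricted analysis in Protocol 13.9. The SAP never attaches it to the subset endpoints. The fault is a mismatch between the two documents in the population analysed.
- A reader might also infer that the true powers, on the protocol's own rates, are 73% and at most 63%. The documents do not support that. They give no 7-day rates by index admission status, and Step 4 shows the admitted subset anywhere from about 30% to 89% with the overall rates unchanged. Even with uniform rates, an exact chi-square calculation reaches about 66%. Dropping patients still in hospital reduces the sample, but it does not settle the unknown rates.
- The SAP is not wholly without an all-patient use of hospitalization. The composites combine it with ED revisits and day hospital visits, and SAP 7.7.2 describes a per-patient 0, 1 or 2+ category. Neither is the quantity that was powered. The composites include other events. The 7.7.2 category counts a direct index admission as the first admission, which cannot fit 20% versus 5% when index admission alone is assumed at 35% versus 50%. It also has no row of its own in Table 17.1.
- The endpoint is secondary and did not set the sample size. Protocol 13.6 promises cautious reading of secondary results, and Table 17.1 reports confidence intervals. This limits the harm, because the interval will show the precision achieved. It does not make the planning figure fit the planned analysis.

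**Conclusion.** The point holds as a protocol–SAP mismatch. The 94% is correct for all 230 patients and applies to neither hospitalization endpoint that the SAP tests.

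Power for those two endpoints cannot be fixed from the documents. It is about 73% and 63% if 20% versus 5% is assumed in each subset, with the latter falling to about 52% or 38% if a quarter or half of admitted patients are still in hospital. With only the overall rates kept, and a common share of 50% to 90% of events in patients not admitted, it is about 48% to 78% and 89% down to 30%. All of these figures rest on the protocol's index admission rates and on the pooled normal approximation. The primary endpoint is unaffected.

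Splitting by index admission also conditions on a post-randomization outcome that the protocol assumes to differ between arms. That is a separate question of bias and is not part of this point.

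**What to change.** Preferred: add to SAP 4.2 and Table 17.1 the all-patient 7-day hospitalization comparison that Protocol 13.9 describes, stating that the index admission is not counted, and attach the 94% to that comparison only. The two subset endpoints can stay beside it.

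Otherwise: state in Protocol 13.7 or the SAP's sample-size section that the 94% does not apply to the two subset endpoints, and give their power as a range with the subset-rate assumption and the assumed proportion still in hospital shown.

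Cost: one more table row in the first case, or a less favourable stated figure in the second. Neither needs extra patients.

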13.8. Analysis of Primary Endpoint

The statistical comparison of the two randomized arms with respect to the primary outcome is comparing the means of the pain score reductions between the two arms. A comparison between two groups will be performed, adjusting for the initial pain score at ED time of placement in a treatment area, biological variables of SCD genotype, age and gender. This analysis will utilize linear regression with pain score reduction as the dependent variable and treatment indicator with pain score at time of placement in a treatment area as covariates (independent variables). Rejection of the null hypothesis stating that coefficient for the treatment indicator is zero will provide evidence for presence of the treatment effect. This comparison will utilize subjects with available measure of the primary outcome. In addition to the statistical hypothesis testing, 95% confidence intervals descriptively summarizing the difference in outcome between the two arms, as well as outcome in each arm will be computed.

Missing Data: Because the outcome data are collected during an ED visit over a time period up to 6 hours, we don't expect missing data due to any subject deaths during this time or withdrawal from the study. However, the pain score reduction may be missing if the pain score at the beginning or the end is not recorded (e.g., if patient left without doing the interview prior to discharge or hospital admission). We will make every effort to prevent missing data on pain score at the beginning and document reasons for missing pain score at final disposition (discharge or admission). If more than 5% of randomized patients have the pain score reduction missing, we will use multiple imputations in the primary analysis to mitigate potential bias of the complete case analysis. This analysis is valid under the missing at random (MAR) assumption. First, an imputation model via linear regression will be developed (based on available data) relating the pain score reduction with a collection of covariates including initial pain score, treatment indicator, baseline characteristics, and possible interactions of covariates with treatment. A total of 1000 data sets with imputations of pain score reduction utilizing the imputation model will be generated. Each of such data sets will be analyzed with linear regression (as described above), and the combined results comparing two groups will be reported by taking into account of variability due to multiple imputations.

Sensitivity analysis: Unfortunately, the MAR assumption cannot be verified with the observed data alone and we will consider sensitivity analysis to examine impact of departure from the MAR assumptions on the treatment effect. We will consider the best and worst scenarios where the worst scenario is to impute the pain score reduction to be zero for patient-specific analgesic protocol and observed maximum pain reduction for the weight-based analgesic protocol and the reverse is used for the best scenario.

